6.1 Interim Analysis

No interim analysis will be conducted.

6.2 Determination of Sample Size

The Final Monograph (21 CFR Part 310 Safety and Effectiveness of Health Care Antiseptics; Topical Antimicrobial Drug Products for Over-the-Counter Human Use) calls for a minimum of 100 observations per treatment. A standard deviation of 1.0 \log_{10}/cm^2 was observed in study EM-05-012760. One-hundred subjects per treatment arm

CDT

provides 94% power using a non-inferiority margin of $0.5 \log_{10}/\text{cm}^2$ with a 1-sided alpha of 0.025.

In the same study, a superiority to the negative control was observed to be approximately $2.5 \log_{10}/\text{cm}^2$, with a lower 95% confidence bound of $2.26 \log_{10}/\text{cm}^2$. A sample size of 30 for the negative control will ensure that the mean for \log_{10}/cm^2 reduction of skin flora relative to Treatment Day baseline will be normally distributed. With 100 observations for the active products and 30 observations for the negative control, the mean observed difference must be greater than $1.62 \log_{10}/\text{cm}^2$ for the lower 95% confidence bound to be greater than $1.2 \log_{10}/\text{cm}^2$. At these sample sizes and the lower 95% confidence bound of $2.26 \log_{10}/\text{cm}^2$, there is 79% power to show superiority to the negative control with a 1-sided alpha of 0.025.

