3.2 Randomization

The left and right test areas on the subject's inguinal region will be assigned according to a computer-generated randomization schedule where each will receive 1 of the 3 study products (see Table 1). Treatment randomization will be balanced between left and right sides. There are 3 different possible combinations of treatments. These are shown below in Table 2.

To provide enough subjects to meet study objectives, the treatment combinations will be randomized in a 6:1:1 ratio for combinations 1 through 3, respectively, at the single recruiting clinical facility. The details of block size will be documented in the final study report.

Baseline and post-prep samplings at 10 minutes and 6 hours will be randomized to three sites within each test area. The same test site randomization will be used on the left and right sides of a subject's body to reduce the possibility of sampling errors.

The Investigator is responsible for ensuring that the study randomization is followed. Randomization envelopes will be provided to the study site.

CDT

Table 1 Study Products

Treatment Code	Study Product	Description
SP	SoluPrep	Contains 2% w/v chlorhexidine gluconate (CHG) and 70% v/v isopropyl alcohol (IPA). 10.5-mL applicator, tinted.
SPFF	SoluPrep FF	Contains 2% w/v chlorhexidine gluconate (CHG) and 70% v/v isopropyl alcohol (IPA) in combination with an acrylate copolymer. 10.5-mL applicator, tinted.
S	Saline	Negative control. Sterile 0.9% saline. 20-mL bottle.

Table 2 Subject Treatments

Treatment Combination	Left and Right Treatment
1	SoluPrep 10.5-mL and SoluPrep FF 10.5-mL (SP + SPFF)
2	SoluPrep 10.5-mL and saline (SP + S)
3	SoluPrep FF 10.5-mL and saline (SPFF + S)

Randomization Plan:

A 3M statistician not assigned to the project will develop a randomization program and generate the randomization code list. The code list will include randomization number, left side treatment, right side treatment, baseline sample site, 10-minute sample site and 6-hour sample site. The randomization assignments will be printed and inserted into security envelopes then tightly sealed.

The Data Manager will strip the treatment assignment from the programs that are used to download the data from Clindex®. This will keep the statistician assigned to the study blinded until data lock.

CDT

Randomization Process:

For each eligible subject to be randomized, the investigator or designee will do the following:

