- Retrieve a randomization envelope with smallest available randomization envelop number.
- Record randomization number onto a Data Collection Sheet (DCS) and/or the electronic Case Report Form (eCRF).
- When the treatments are applied, record onto a DCS and/or the eCRF; left side treatment applied, right side treatment applied, baseline sample site, 10-minute sample site and 6-hour sample site.
- Subjects will continue to be randomized until a minimum of 100 observations (with a baseline that meets the Treatment Day requirement) from each of the active treatments and 30 observations from the saline control (with a baseline that meets the Treatment Day requirement) have been collected.

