5.2 Modified Intent-To-Treat Population (MITT)

A MITT data set will be used for primary efficacy analyses. All subjects who meet baseline requirements on a bilateral side will be included in the analysis for that bilateral side. However, the primary analyses involve a linear regression at the 10-minute post-treatment time point and calculation of return to baseline at 6 hours. These analyses require both baseline and 10-minute recovery for treatment effect or baseline and 6-hour recovery data for return to baseline percentage calculation. There is no scientific basis for imputation of these missing values. Fortunately, missing values are not expected. There was no missing data for the 2346 microbiological samples taken in the pivotal study conducted at this site for SoluPrep FF. The exclusion of subjects who do not meet baseline requirements and who are missing recovery data at either the 10-minute sampling time point or the 6-hour sampling time point (post-treatment) times makes this data set a modified intent-to-treat data set.

The baseline bacterial count requirements are in the range of 5.00 to 7.50 \log_{10}/cm^2 on the groin. The acceptability of each bilateral baseline will be assessed separately for inclusion in the study.

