### **1.5 Study Population**

Healthy male and female volunteers, 18 years of age or older, with no dermatological conditions on the test sites, or known history of sensitivity to acrylates, CHG- or alcohol-containing products, medical tapes, metals, natural rubber latex, vinyl, or skin-marking inks, will be enrolled into this study. A sufficient number of subjects will be enrolled in the screening phase, such that approximately 100 applications of the investigational product (10.5-mL tinted) and the active control (10.5-mL tinted), in addition to approximately 30 applications of the negative control, are evaluable for efficacy on the inguinal region (groin) at completion of the study. In total, 230 evaluable applications of investigational product, active control, and negative control would require 115 test subjects, utilizing both the right and left sides of the inguinal region. With the expectation that 15% of subjects will not meet treatment day baseline requirements, it is anticipated that 135 subjects will need to be treated. Subjects must satisfy all Screening Day and

3M Confidential

Document Name: CLIN-PROT-ICH-US-05-658998

Clinical and Non-Clinical: CLIN-INDEX-3M-SPON-US-05-014624

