## 8. STATISTICS

### 8.1 Sample Size Justification

The Final Monograph (21 CFR Part 310 Safety and Effectiveness of Health Care Antiseptics; Topical Antimicrobial Drug Products for Over-the-Counter Human Use) calls for a minimum of 100 observations per treatment. A standard deviation of  $1.0 \log_{10}/\text{cm}^2$  was observed in study EM-05-012760. One-hundred subjects per treatment arm provides 94% power using a non-inferiority margin of  $0.5 \log_{10}/\text{cm}^2$  with a 1-sided alpha of 0.025.

In the same study, a superiority to the negative control was observed to be approximately  $2.5 \log_{10}/\text{cm}^2$ , with a lower 95% confidence bound of  $2.26 \log_{10}/\text{cm}^2$ . A sample size of 30 for the negative control will ensure that the mean for  $\log_{10}/\text{cm}^2$  reduction of skin flora relative to

[name]

Treatment Day baseline will be normally distributed. Power was assessed through simulation using an assumed superiority of  $2.26 \log_{10}/\text{cm}^2$  (the lower 95% confidence bound observed in study EM-05-012760), sample sizes of 30 for the negative control and 100 for the active treatments, and the standard deviation of  $1.0 \log_{10}/\text{cm}^2$  mentioned above. All 1000 simulations had a lower bound for superiority greater than  $1.2 \log_{10}/\text{cm}^2$ .

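### SAP 6.2 states 79% power for superiority to saline; its own inputs give about 99.9%, in line with its 1.62 threshold and the protocol's simulation

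*SAP*

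**What the plan says.** SAP section 6.2 takes an SD of 1.0 log10/cm² from study EM-05-012760. For non-inferiority it says that 100 per arm "provides 94% power using a non-inferiority margin of" 0.5 at one-sided alpha 0.025.

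For superiority to saline, with 100 active and 30 saline observations, it says "the mean observed difference must be greater than" 1.62 for the lower 95% bound to clear 1.2. It then takes 2.26, the lower confidence bound seen in the earlier study, as the true difference, and concludes that "there is 79% power to show superiority to the negative control with a 1-sided alpha of 0.025".

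Protocol section 8.1 uses the same difference (2.26), SD (1.0) and sample sizes (100 and 30). It reports a simulation instead: "All 1000 simulations had a lower bound for superiority greater than" 1.2. It states no alpha for that simulation.

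On the enrolment forecast, protocol section 1.5 says that 230 evaluable applications "would require 115 test subjects, utilizing both the right and left sides of the inguinal region". It expects 15% of subjects to miss the treatment-day baseline requirement and so anticipates treating 135. SAP section 3.2 says that "the treatment combinations will be randomized in a 6:1:1 ratio for combinations 1 through 3".

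**The concern.** Superiority to saline by the 1.2 margin is part of the primary objective. For this one comparison the SAP reports power just under 80%, while the protocol reports success in every simulated trial on what appear to be the same assumptions. Both cannot be right.

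A reader of the SAP alone would take a near-certain comparison for a marginal one. A reader of both documents cannot tell whether 79% is a slip or reflects a larger SD or smaller effect that the SAP does not disclose. If an undisclosed SD were the reason, the non-inferiority power would be in doubt too.

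**Working it through.** **Inputs (SAP 6.2).** SD 1.0; n = 100 active and 30 saline; true difference 2.26; margin 1.2; one-sided alpha 0.025. Observations are treated as independent and the baseline covariate is ignored, as the SAP's own figures appear to do.

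**1. Is SD 1.0 the SAP's working value?** Non-inferiority with 100 per arm and margin 0.5:
- SE = 1.0 × √(1/100 + 1/100) = 0.141, and 0.5/0.141 = 3.54.
- Power = 94.2% (normal) or 94.0% (noncentral t, df 198).

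The stated 94% reproduces, so SD 1.0 is in use.

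**2. The 1.62 threshold.**
- SE = 1.0 × √(1/100 + 1/30) = 0.208.
- Threshold = 1.2 + t(0.975, 128) × SE = 1.2 + 1.979 × 0.208 = 1.61.

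The stated 1.62 differs by about 0.01 and implies an SD of about 1.02. This is immaterial and again points to SD 1.0.

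**3. Superiority power.**
- (2.26 − 1.2)/0.208 = 5.09.
- Power = 99.90% (noncentral t, df 128) or 99.91% (normal); simulation gives 99.9%.

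The stated 79% does not reproduce.

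**4. Check against the SAP's own threshold.** (2.26 − 1.62)/0.208 = 3.07, so the probability of an observed difference above 1.62 is 99.9%.

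**5. Check against protocol 8.1.** The probability of 1000 successes in 1000 is 0.999^1000 ≈ 0.37 at 99.9% power, and 0.79^1000 ≈ 4e-103 at 79%.

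**6. What could produce 79%?**

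| Change, other inputs as stated | Power |
|---|---|
| One-sided alpha 0.05 | 99.97% |
| One-sided alpha 0.005 | 99.3% |
| 30 vs 30 observations | 98.4% |
| 1.62 used as the margin, one-sided 0.025 | 86–87% |
| 1.62 used as the margin, two-sided 0.025 | 78.9% (t), 79.8% (normal) |

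Solving for 79% one input at a time gives:
- an SD of 1.83;
- or a true difference of 1.78;
- or 7 to 8 saline observations, with 100 active.

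An SD of 1.83 contradicts the rest of the section: the threshold would be 1.95 instead of 1.62, and non-inferiority power would be 49% instead of 94%. The other two values appear nowhere in the documents.

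The last table row does reach 79%. It takes the success threshold as the margin, so the confidence half-width is counted twice, and it halves alpha. That is a possible origin, which the documents do not confirm, and it would be a calculation error.

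**7. Enrolment forecast (secondary).** Under 6:1:1, 2 of every 8 subjects receive saline on one side, so the saline fraction is 0.25 per subject.
- 115 × 0.25 = 28.75 saline sides; 30/0.25 = 120 fully evaluable subjects are needed.
- 115/0.85 = 135, which is the protocol's treated number.
- At 135 treated, if each failing subject loses both sides (or 15% of sides fail): 135 × 0.25 × 0.85 = 28.7 evaluable saline sides expected.
- If each failing subject loses one side: 135 × 0.25 × 0.925 = 31.2.

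Protocol 1.5 does not say which applies. SAP section 5.2 judges sides individually: "The acceptability of each bilateral baseline will be assessed separately for inclusion in the study".

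**The case against.** The strongest objection concerns importance. The error is conservative. The 100 per active arm rests on the Final Monograph minimum and the 30 saline observations on a statement about normality, so neither depends on the 79%. Protocol 8.1 already reports the favourable result, and the remedy is one number in a justification paragraph. All of this stands, and it confines the point to a text correction. It does not make the figure right: the SAP states a wrong power for a primary comparison and disagrees with the protocol.

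A second objection is that 79% can be reached without altering the SD, the true difference or the sample sizes, by using 1.62 as the margin with a two-sided alpha of 0.025. That is correct arithmetic. It supports a slip over undisclosed assumptions and makes replacing the number the likelier remedy.

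Third, the forecast in protocol 1.5 is worded as approximate and cannot leave the trial short by itself. SAP 3.2 says "Subjects will continue to be randomized until a minimum of 100 observations" per active product and 30 for saline qualify, and protocol 3.3 provides 10 blocks of 16, or 160 slots. This also stands. The forecast is a clarification, would not merit a comment alone, and is no evidence about the 79%.

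Finally, asking protocol 8.1 to state its alpha is a matter of completeness, since one-sided values from 0.005 to 0.05 leave power at 99.3% or more.

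**Conclusion.** The concern holds. On the SAP's stated inputs, power to show superiority to saline is about 99.9%, so the stated figure is about 21 percentage points too low. It is incompatible with the threshold in the sentence before it and with the protocol's simulation. The result assumes independent observations, a common SD of 1.0 and no covariate adjustment. Confidence is high, because two other figures in the same section confirm the SD.

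The consequence is limited to the justification text: the sample size, margin, analysis and decision rule are unaffected. The enrolment forecast is a minor inconsistency with the allocation ratio and puts no evaluable count at risk.

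**What to change.** In SAP 6.2, replace 79% with the recomputed power (greater than 99%). If 79% came from different inputs, state them and explain how they fit the 1.62 threshold and the 94% non-inferiority power. Reconcile the result with protocol 8.1, and add there the alpha used in the superiority simulation.

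In protocol 1.5, derive the forecast from the 6:1:1 ratio and say whether a 15% baseline failure means the loss of one side or both.

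The cost is text only. The sample size, randomization list, margin and analysis stay as they are.

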6.3 Handling of Dropouts and Missing Data

There will be no imputation of microbiological data because there is no scientific basis for such imputation.

6.4 Validation Plan

Programs were developed for the pivotal studies for SoluPrep FF. Programs were written by both 3M and the Contract Research Organization (CRO) hired by 3M, yielding identical results. The current study is very similar to those studies and the previously developed programs can be used with minor modifications. Validation of statistical programs and output will be through an independent review of the code and output by a statistician not assigned to this study.

7. SUMMARY OF STUDY POPULATION

CDT

7.1 Subject Disposition

Subject enrollment, including number of subjects screened, number of subjects randomized and the reasons for screen failures, will be summarized by treatment group and overall.

Subject disposition, including the number and percentage of subjects included in each analysis data set (ITT, MITT or PP), as well as reasons for exclusion from the PP data set, will be summarized by treatment group and overall.

Study completion status (completed the study or discontinued early from the study), as well as the primary reason for study discontinuation, will be summarized by treatment group and overall.

7.2 Protocol Deviations

Protocol deviations are any departure from the protocol. Protocol deviations that affect the evaluability of subjects will be reviewed during a blinded review process and documented before data lock and study analysis. Deviations will be summarized by categories, treatment group and overall. Listing of protocol deviations will also be provided.

7.3 Baseline and Demographic Characteristics

Descriptive summary statistics will be provided for demographic characteristics for each treatment group and overall. For continuous variables, the number of subjects, mean, standard deviation, median, minimum and maximum will be provided. For categorical variables, the number and percentage of subjects in each demographic category will be summarized.

7.4 Treatment Duration and Compliance

CDT

Since the treatments will be administered by study staff, subject compliance with respect to treatment compliance is not an issue in this study. Treatment duration is 6-hours, \pm 30 minutes. Therefore, treatment exposure and compliance will not be summarized or listed.

The subjects may leave the facility after the 10-minute post treatment microbial samples are taken. They will be queried before the 6-hour sample is taken to determine if they have followed the instructions to avoid showering, tub-bathing, swimming, vigorous physical activity that may cause sweating, and any other activity that may compromise the integrity of the test sites.

8. EFFICACY ANALYSIS

8.1 Primary Efficacy Analysis

The average treatment effect (ATE) for the investigational product will be estimated using a linear regression of the 10-minute post-treatment bacterial count (\log_{10} scale) on the additive effect of a treatment indicator and the baseline measurement (\log_{10} scale). The lower bound of the 95% confidence interval for the additive treatment effect must not include the investigational product being more than $0.5 \log_{10}/\text{cm}^2$ lower than the positive control.

The ATE of the test product compared to the negative control is estimated as the contrast of treatment effect of negative control minus the treatment effect of the test drug in the linear regression. Likewise, the ATE of the active control compared to the test product is estimated as the contrast of treatment effect of test product minus the treatment effect of the active control in the linear regression. Superiority to negative control uses a margin of $1.2 \log_{10}/\text{cm}^2$, which would be demonstrated by a lower bound of the 95% confidence interval for the contrast to exceed $1.2 \log_{10}/\text{cm}^2$.

An example code for the analyses specified above is shown below:

Proc Mixed data=D_14624.LogMicro;

Class Treatment;

CDT

```
Where Timepoint=1 and Treatment in (1 2);  
Model LogRecovery=Treatment LogBaseline/ddfm=kr;  
Lsmeans Treatment/cl;  
Run;
```

The percent of samples for which the 6-hours post treatment recovery is lower than the baseline recovery will be calculated by active product. Thus, if \log_{10} reduction is >0 the sample has not returned to baseline. The Final Monograph requires that these percentages be 100.

An example code for percentage return to baseline is shown below:

Proc Format;

```
value Return      -5-0='Returned to Baseline'  
                 0.0001-8='Did not Return to Baseline';  
run;
```

Proc Freq data=D_14624.LogMicro;

```
Where Timepoint=2;  
Tables LogReduction*Treatment/nopercent norow;  
format LogReduction return.;
```

Run;

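### The non-inferiority rule tests the wrong end of the confidence interval: on a count scale where lower is better, it passes a worse product and fails a better one.

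*SAP*

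**What the plan says.** The primary immediate-effect analysis in SAP 8.1 is a "linear regression of the 10-minute post-treatment bacterial count" (log10 scale) on treatment and baseline. The example code has the same response: "Model LogRecovery=Treatment LogBaseline/ddfm=kr".

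The non-inferiority rule is: "The lower bound of the 95% confidence interval for the additive treatment effect must not include the investigational product being more than" 0.5 log10/cm² lower relative to the positive control.

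The next paragraph gives two contrasts. For saline it is the "contrast of treatment effect of negative control minus the treatment effect of the test drug in the linear regression", with success if the lower 95% bound exceeds 1.2. For the active control it is the "contrast of treatment effect of test product minus the treatment effect of the active control in the linear regression".

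Protocol 8.2.1 has the same rule and the same contrasts, so it does not correct the SAP. SAP 6.2 says that 100 per arm "provides 94% power using a non-inferiority margin of" 0.5 log10/cm² "with a 1-sided alpha of 0.025".

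**The concern.** The response counts surviving bacteria, so a lower value is better. With the contrast taken as test minus active control, the unfavourable direction is positive, and non-inferiority requires the upper bound to lie below +0.5. The written rule instead looks at the lower bound and requires it to lie above −0.5. That rules out only a SoluPrep that kills substantially more than the control.

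This is the pass/fail rule for the first part of the primary objective. Applied as written, it gives no protection against declaring an inferior product non-inferior, and it would fail a product clearly better than its comparator. SAP 3.3 has the programming done on dummy treatment assignments, so a reversed direction need not show until unblinding. Choosing the bound at that point would be a post hoc decision on a primary criterion.

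**Working it through.** **Inputs (SAP 6.2).** SD 1.0 log10/cm²; 100 observations per active arm; margin 0.5; one-sided alpha 0.025, which is one end of a two-sided 95% interval. Let d be the true difference, SoluPrep minus SoluPrep FF, in 10-minute log10 recovery; d > 0 means SoluPrep is worse.

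**Standard error.** SE = √(1.0²/100 + 1.0²/100) = √0.02 = 0.1414. Half-width of the 95% interval = 1.96 × 0.1414 = 0.277.

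**The plan's own power figure.** The plan states no true difference, so I assume d = 0. Power = Φ(0.5/0.1414 − 1.96) = Φ(1.576) = 94.2%. The noncentral t with 198 df gives 94.0%. The stated 94% is reproduced.

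**The two rules.**
- As written: estimate − 0.277 > −0.5, that is, estimate > −0.223. Pass probability = Φ((d + 0.223)/0.1414).
- Corrected: estimate + 0.277 < +0.5, that is, estimate < +0.223. Pass probability = Φ((0.223 − d)/0.1414).

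| True d (SoluPrep − SoluPrep FF) | Rule as written | Corrected rule |
|---|---|---|
| −1.0 (better) | about 0% | about 100% |
| −0.5 (better) | 2.5% | about 100% |
| −0.25 (better) | 42.4% | 99.96% |
| 0 | 94.2% | 94.2% |
| +0.25 (worse) | 99.96% | 42.4% |
| +0.5 (worse, at the margin) | about 100% | 2.5% |
| +1.0 (worse) | about 100% | about 0% |

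The type I error at the margin is therefore about 100% where the plan intends 2.5%.

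**Checks.** A simulation of the covariate-adjusted model (4,000 runs per value of d; assumed baselines uniform on 5.0 to 7.5 and an assumed slope of 0.3) gave, written versus corrected: 100% versus 2.5% at d = +0.5, 2.5% versus 100% at d = −0.5, 100% versus 0% at d = +1, and 0% versus 100% at d = −1. Most subjects receive both active products, so I also let the within-subject correlation range from 0 to 0.7 (an assumption). With SE = √(2(1 − ρ)/100), the SE falls from 0.141 to 0.077. Pass rates at d = ±0.5 and ±1 are unchanged, and so is the reversal.

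**Can another reading rescue the sentence?**
- *Response is recovery, contrast is test minus active (as written).* The lower-bound rule excludes only a better product.
- *Response is log reduction, contrasts as written.* The rule against the active control becomes correct. But negative control minus test would then be negative for any product that works better than saline, so an effective product could not meet the requirement of a lower bound above 1.2.
- *Response is recovery, contrast is active minus test.* The rule becomes correct, but neither document writes this contrast for the two active products.

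No single reading of the text as it stands makes both rules in the section sound. The example code does not settle the direction: its `Lsmeans` line requests an interval for each treatment mean and no difference.

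**The case against.** The best defence is that the section uses a benefit-oriented convention. The effect of the test product compared with saline is written as saline minus test, so that positive favours the product named first. The effect of the active control compared with the test product is written as test minus active, which follows the same pattern. The rule sentence concerns the effect of the investigational product. By that convention its effect against the positive control would be active minus test, and a lower bound above −0.5 would then be a correct rule with recovery as the response. The objectives, the margin and the one-sided power calculation all describe ordinary non-inferiority, so a reversed test is plainly not intended.

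The point about intent stands. The rescue does not, because it needs a contrast that neither document states. The only SoluPrep versus SoluPrep FF contrast written down runs the other way, and nothing in the rule says that lower means less effective.

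It is also fair that the pass rates describe this criterion alone. SoluPrep must also beat saline by 1.2. Assume that SoluPrep FF beats saline by 2.26 to 2.5 (SAP 6.2), with SD 1.0 and 100 versus 30 observations, so SE = √(1/100 + 1/30) = 0.208. The observed difference from saline must then exceed 1.2 + 1.96 × 0.208 = 1.608. A SoluPrep 1.0 log10 worse than SoluPrep FF would be 1.26 to 1.5 better than saline and would meet the criterion about 5% to 30% of the time. One 0.5 worse would be 1.76 to 2.0 better and would meet it about 77% to 97% of the time. The saline criterion, and the separate 6-hour persistence requirement, may therefore stop a very poor product. Neither tests the 0.5 margin against the active control, and the saline criterion offers little protection at that margin.

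**Conclusion.** The concern holds. As written in both documents, the non-inferiority rule bounds the favourable side of the comparison. At the plan's own inputs it passes a product 0.5 log10 worse about 100% of the time (2.5% intended) and one 0.5 log10 better 2.5% of the time (about 100% intended). These rates use a normal approximation with SD 1.0 and 100 per arm and refer to this criterion alone; the reversal itself does not depend on those values. The sample size and the 94% power are unaffected, because the two rules have equal power at zero difference. The fault lies in the written rule and need not reflect the sponsor's intent, but a primary decision rule must be correct as written. This must be fixed before data lock.

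**What to change.** Replace the rule in SAP 8.1 and protocol 8.2.1 with: *Non-inferiority is demonstrated if the upper bound of the two-sided 95% confidence interval for SoluPrep minus SoluPrep FF in 10-minute log10/cm² recovery, adjusted for baseline, is less than +0.5.* Equivalently, define the contrast as SoluPrep FF minus SoluPrep and require the lower bound to exceed −0.5. Either form will do, provided the contrast, its sign and the bound are stated together.

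Add a statement to the example code that requests this treatment difference with its confidence limits in the stated direction. Leave the saline rule as it is; its orientation is correct.

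The cost is one sentence in each document and one line of code. No further subjects or data are needed.

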3. INVESTIGATIONAL PLAN

3.1 Study Design

This is a randomized, controlled, third-party blind, single-center study in healthy volunteers where each subject receives 2 of the 3 possible study products on the groin. The study staff performing the bacterial enumeration and the statistician performing the analysis will be blinded to the study products.

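### The example code for the 10-minute analysis in SAP 8.1 does not do what the text specifies: it keeps two of three treatments, gives no contrast interval, and has no subject term for paired sides

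*SAP*

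**What the plan says.** SAP 8.1 regresses the 10-minute log count on treatment and baseline and rests both comparisons on a contrast from that regression.

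- **Non-inferiority:** the contrast is the "contrast of treatment effect of test product minus the treatment effect of the active control in the linear regression". The rule reads "The lower bound of the 95% confidence interval for the additive treatment effect must not include the investigational product being more than" 0.5 below the positive control.
- **Superiority:** the contrast is negative control minus test product, and the lower 95% limit must exceed 1.2. SAP section 4 extends superiority to both active products.

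Protocol 8.2.1 repeats the 8.1 prose and gives no code.

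The SAP introduces its code with "An example code for the analyses specified above is shown below". The working lines are:

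- "Where Timepoint=1 and Treatment in (1 2"
- "Model LogRecovery=Treatment LogBaseline/ddfm=kr"
- "Lsmeans Treatment/cl"

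On the design, SAP 3.1 says that "each subject receives 2 of the 3 possible study products on the groin".

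**The concern.** Three features of the code do not fit the text above it.

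1. **Two treatments kept.** SoluPrep versus SoluPrep FF and SoluPrep versus saline together need three products, so one run covers at most one comparison. Codes 1 and 2 are not mapped to products. Table 1 labels the products SP, SPFF and S, and the numbers 1 to 3 in Table 2 denote treatment combinations.
2. **No difference requested.** In PROC MIXED, LSMEANS with CL alone prints limits for each arm's adjusted mean. Limits for a difference need DIFF or ESTIMATE with CL, or SOLUTION with CL for the coefficient. None is present.
3. **No subject term.** There is no RANDOM or REPEATED statement, so a subject's left and right sides enter as unrelated observations. The prose does not mention subject either.

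This is the only code given for the primary 10-minute analysis, and SAP 6.4 relies on adapting existing programs and on an independent review of code and output. A template that cannot yield the decision quantity is a poor reference for that review. It also leaves open whether the interval comes from one three-treatment fit or from separate pairwise fits.

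**Working it through.** **Inputs.** SD 1.0, 100 observations per active product, 30 saline, margins 0.5 and 1.2, one-sided alpha 0.025 (SAP 6.2). Allocation 6:1:1 to SP+SPFF, SP+S and SPFF+S (SAP 3.2). Assumed: 90, 15 and 15 subjects with both sides evaluable. This is the 6:1:1 split that gives 30 saline sides, and it gives 90+15 = 105 sides per active product. Within-subject correlation ρ is not in the documents, so I use 0, 0.2, 0.5 and 0.7. SD 1.0 is treated as the residual SD, and estimation of the baseline slope is ignored.

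**The plan's own figure.** SE = √(2/100) = 0.1414. Power = Φ(0.5/0.1414 − 1.96) = Φ(1.576) = 0.942, which matches the stated 94%. That calculation treats all observations as independent.

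**What the code prints against what is needed.** At 100 per arm, an arm-level limit has half-width 1.96 × 1.0/√100 = 0.196. The interval for the difference has half-width 1.96 × 0.1414 = 0.277. The printed limits are not on the scale of the margin.

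**SoluPrep versus SoluPrep FF.**
- Independence: SE = √(2/105) = 0.138.
- Random subject effect, three treatments: variance = 2(1−ρ²)/(105+90ρ). At ρ = 0.5 this is 1.5/150 = 0.0100, so SE = 0.100.

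**Saline minus SoluPrep, with a subject effect.**
- Three treatments: variance = (1−ρ²)(a+c+2b)/(ac−b²) + ¼ × (the SoluPrep versus SoluPrep FF variance), with a = 210−180ρ, b = −30ρ, c = 30. At ρ = 0.5: 0.75 × 120/3375 + 0.0025 = 0.0292, so SE = 0.171.
- Pairwise subset: variance = (a+c+2b)/(ac−b²), with a = 90+15/(1−ρ²), c = 15+15/(1−ρ²), b = −15ρ/(1−ρ²). At ρ = 0.5: 125/3750 = 0.0333, so SE = 0.183.

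| ρ | SP vs SPFF, independence | SP vs SPFF, subject effect | Saline − SP, three-treatment | Saline − SP, pairwise | Variance ratio, pairwise to three-treatment |
|---|---|---|---|---|---|
| 0 | 0.138 | 0.138 | 0.207 | 0.207 | 1.00 |
| 0.2 | 0.138 | 0.125 | 0.199 | 0.201 | 1.02 |
| 0.5 | 0.138 | 0.100 | 0.171 | 0.183 | 1.14 |
| 0.7 | 0.138 | 0.078 | 0.138 | 0.159 | 1.31 |

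**Whether the independence error bar is wrong or merely inefficient.** The simple difference of arm means has true variance 2/105 − 2ρ × 90/105². At ρ = 0.5 that is 0.01905 − 0.00816 = 0.01088, an SE of 0.104. The independence model would report 0.138 for an estimate whose real SE is 0.104. With positive correlation the reported interval is too wide.

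**The case against.** The code is labelled an example, and the prose gives the model, the direction of each contrast, the confidence level and the margins. SAP 6.4 says the programs come from earlier studies, where sponsor and CRO versions agreed, and will be reviewed independently. A competent programmer would add the missing option, and the WHERE line can be rerun for each pair. This stands in part: the estimand is not missing. Rerunning by pair still yields no difference interval without DIFF or ESTIMATE, and the subject term is absent from both code and prose.

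The precision figures depend on a correlation that the documents do not give. At ρ = 0 they vanish, and the loss from pairwise subsetting exists only once subject is in the model. At planning values it would not change the superiority decision: even under independence with 100 and 30 observations, SE = √(1/100+1/30) = 0.208, and Φ((2.26−1.2)/0.208 − 1.96) is about 0.999. (SAP 6.2 prints 79%, which is a separate discrepancy.) All of this stands.

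A reader might infer that non-inferiority would be judged by comparing the two arm-level intervals, at a cost in power. No section proposes that, and the prose requires the contrast interval. A reader might also infer that pairing left out of the model makes false claims more likely. For positive correlation the working shows the opposite.

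**Conclusion.** The point holds as a mismatch between code and text, together with a model that treats paired sides as independent. It concerns the two 10-minute comparisons only.

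That the printed code gives no contrast interval and covers only two products follows from reading it and rests on no assumption. The size of the error-structure problem is conditional. For SoluPrep versus SoluPrep FF, the SE is 0.138 under independence against 0.125 to 0.078 with a subject effect for ρ from 0.2 to 0.7, given SD 1.0 and 90/15/15 subjects, with no difference at ρ = 0. With subject in the model, pairwise subsetting costs 0%, 2%, 14% and 31% in variance for the saline contrast at ρ of 0, 0.2, 0.5 and 0.7.

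A reader might conclude that the trial cannot answer its primary questions. The documents do not support that, because the prose specifies the contrasts. Nor do they show that residual variance differs by product, so treatment-specific variances are not part of this point.

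**What to change.** Replace the example in SAP 8.1 before unblinding, and add the subject effect to the prose there and in protocol 8.2.1.

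- Keep all three treatments and state the codes, for example 1 = SP, 2 = SPFF, 3 = S.
- Fit one model: `model LogRecovery = Treatment LogBaseline / ddfm=kr;` with `random Subject;` and Subject in the CLASS statement.
- Request each contrast with limits:
  - `estimate 'SP - SPFF' Treatment 1 -1 0 / cl;` Non-inferiority if the upper 95% limit is below 0.5. On log recovery a higher value is worse, so the upper limit decides. Say so explicitly, because the prose speaks of a lower bound.
  - `estimate 'S - SP' Treatment -1 0 1 / cl;` Superiority if the lower limit is above 1.2.
  - `estimate 'S - SPFF' Treatment 0 -1 1 / cl;` Same rule, covering the second active product named in SAP section 4.

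The cost is a text and code edit and a slightly more complex model. No new data and no change in sample size are needed.
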